1. STUDY IDENTIFICATION

Unique Protocol Identification Number: 2020-07182 Brief Title: MIRAA – implementation of intensive rehabilitation of aphasia and/or apraxia of speech in Swedish healthcare Official Title: MIRAA – A national study on intensive rehabilitation of aphasia and apraxia of speech following stroke

2. STUDY STATUS

Study Type: Interventional
Record Verification: April 2021
Overall Status: Recruiting
Study Start: March 10, 2021 [Actual]
Primary Completion: December, 2022 [Anticipated]
Study Completion: December, 2024 [Anticipated]

4. OVERSIGHT

Studies a U.S. FDA-regulated Drug: No Studies a U.S. FDA-regulated Device: No Device Product Not Approved or Cleared by U.S. FDA: No U.S Food and Drug Administration IND or IDE: No HUMAN SUBJECTS REVIEW Human subjects Protection Review Board Status: Submitted, approved Board Approval Number: 2020-07182 Board Name: Swedish Ethical Review Authority Board Affiliation: Etikprövningsmyndigheten [contact] Email: [contact]
Address: [name]
Data Monitoring: Yes
FDA Regulated Intervention: No
Section 801 Clinical Trial: No

5. STUDY DESCRIPTION

Brief Summary: Positive outcomes have been shown following intensive treatment of speech and/or language impairment post stroke, but how to design intensive treatment programs to achieve optimal recovery and neuroplasticity changes needs to be further researched. The purpose of the MIRAA (Multimodal Intensive Rehabilitation of Aphasia and Apraxia of Speech) project is to study feasibility of intensive intervention for acquired aphasia and apraxia of speech (AOS) after stroke in the regular Swedish healthcare according to the updated national guidelines from the Swedish National Board of Health and Welfare (Socialstyrelsen, 2018).

Detailed Description: According to the Swedish National Board of Health and Welfare's guidelines for stroke care, persons with aphasia shall be offered intensive rehabilitation by speech-language pathologists. The aphasia rehabilitation is however sparse and unevenly distributed over the country as reported by the Swedish Aphasia Foundation (Afasiförbundet, 2015). People with aphasia are seldom offered long-term treatment and intensive therapy is rarely offered (Blom Johansson, Carlsson et al., 2011; Palmquist, 2018). Intensive treatment is defined as at least 4h/week by the National Board of Health and Welfare, but higher intensity can be beneficial if tolerated by the patient. "It is not completely clear in which phase after stroke the intensive treatment should be offered but it seems more adequate in the sub-acute or chronic phase since a number people will not be able to participate in intensive treatment in the acute phase." (Socialstyrelsen, National guidelines for stroke care, p. 41–42).

Multimodal Intensive Rehabilitation of Aphasia and Apraxia of speech, MIRAA, is a modified ICAP intervention program developed in the applicant's research group. MIRAA consists of a selection of evidence-based and/or well-established methods for speech and language rehabilitation as well as computer training. The training is both individual and group based, including communication between participants to promote transfer to real-life situations. Rehabilitation is based on principles that have been shown to promote neuroplasticity changes, such as high training intensity and multiple repetitions of tasks, for

learning and relearning after brain injury. The intervention is goal-driven and individualized for high saliency, with focus on each participant's difficulties with language, speech and communication.

Speech and Language Pathologists (SLPs) all over Sweden working with aphasia and/or AOS following stroke are offered to participate in the study. At the time of recruitment, SLPs are invited to respond to a questionnaire about their current practice. SLPs accepting to participate are offered a 2-day workshop and recurring sessions containing introduction to and training in the MIRAA program as well as information about the logistics of the study.

The SLPs participating in the study recruit participants with aphasia/AOS from their waiting and offer them a six-week MIRAA rehabilitation program consisting of a combination of individual treatment and group session and computer-assisted/homework training, with the goal level of 60 hours. The content of the program is individually adapted to clinics and participants. Participation in the study is consecutively offered to all individuals with speech language impairment post stroke that meet the inclusion criteria.

Following administration of the MIRAA-program including pre- and post-testing, participating SLPs will complete a questionnaire on their experiences of delivering the intensive intervention and factors hindering and facilitating implementation. Participants with aphasia/AOS and their next of kin will also provide information about their experiences through questionnaires and semi structured interviews, focus groups interviews and participant observations.

All participants are tested pre- post and at follow-up by a speech and language pathologist. Behavioral tests consist of quantitative measurements of speech, language, communication, cognition and quality of life. Part of the testing (TAX and CAT informative speech) is video-recorded for analysis after testing.

Background data are obtained noting sex, age, handedness, education level, language history aphasia type and severity and AOS, time since onset, mental fatigue, social life, number of strokes and earlier intensive rehabilitation at the time of the first assessment.

A subgroup of participants and SLPs from five clinics distributed over varying types of clinics reflecting the diversity among the clinics (inpatient care, primary care) take part in semi-structured interviews based on interview guides combined with focus group interviews and participant observations during one day of the last week of the intensive program

focusing on facilitating and hindering factors for complying with an intensive intervention program like MIRAA.

A group consisting of SLPs not being able to participate in the study will form a focus group and discuss the specific factors hindering participation in the study in their respective settings.

The primary aim of this project is to explore the feasibility for national implementation of an intensive comprehensive intervention program for aphasia and AOS following stroke (MIRAA) in Swedish health care.

- What are facilitating or hindering factors for SLPs and their patients in the subacute and chronic phase post stroke with aphasia and/or AOS to comply with an intensive intervention program like MIRAA?

- How do participants, next of kin and SLPs experience intensive training in terms of effects and satisfaction with the program and with the implementation?

A secondary aim is to examine whether short-term and / or long-term effects on language, speech, communication and quality of life after intensive rehabilitation can be demonstrated. - Can treatment effects regarding speech and/or language be detected when comparing the control group with the intervention group after six weeks of intensive intervention? - Can treatment effects regarding communication and quality of life be detected when comparing the control group with the intervention group after six weeks of intensive intervention?

- Can long-term treatment effects on speech, language, communication and quality of life four months post intervention be detected?

Following clinics participate in the study:

- Aleris Rehab Station, Stockholm
- Dalen, Capio Rehab, Stockholm
- Farsta logopedmottagning, SLSO, Stockholm
- Fysrehab, Lidköping
- Logopedmottagningen Helsingborg och Ängelholm
- Logopedienheten, Södra Älvsborgs sjukhus, Borås
- Logopedkliniken, Danderyds sjukhus, Stockholm
- Logopedbyrån Dynamica AB, Stockholm, Gustavsberg och Södertälje
- Neurologimottagningen, Skånes universitetssjukhus, Lund

- Neurorehab, Vrinnevisjukhuset, Norrköping
- Närhälsan Gamlestadstorgets rehab, Göteborg
- Närhälsan Gibraltar rehabmottagning, Göteborg
- Närhälsan Angered, Rehabmottagning, Göteborg
- Närhälsan Frölunda Rehabmottagning, Göteborg
- Olivia Rehabilitering, Danderyd
- Rehab City Lidingö, Stockholms Läns sjukhusområde
- Rehabiliteringscentrum, region Jönköping
- Rehabenheten, Sjukhusen i väster, Göteborg och Kungälv
- VO Neurologi, Skånes universitetssjukhus, Lund
- Sävedalen rehabmottagning, Partille
- Vällingby logopedmottagning, SLSO Västra, Stockholm
- Specialistrehabiliteringsenheten, Uppsala

6. CONDITIONS AND KEYWORDS

Primary Disease or Condition Being Studied in the Trial, or the Focus of the Study:

- 1. Aphasia
- 2. Apraxia of Speech

Keywords:

- 1. Intensive Rehabilitation
- 2. Neuroplasticity
- 3. Implementation in healthcare
- 4. Stroke guidelines
- 5. ICAP (Intensive Comprehensive Aphasia Program)
- 6. MIRAA (Multimodal Intensive Rehabilitation of Aphasia and Apraxia of Speech)

7. STUDY DESIGN (INTERVENTIONAL)

Primary Purpose: Treatment

Study Phase: N/A

Interventional Study Model: Parallell

Model Description: Cluster randomized clinical trial with two parallel arms.

Number of Arms: 2
Masking: Investigator
Masking description: Block randomized sealed envelopes handled by external coordinator.
Allocation: Randomized
Enrollment: 70 participants with aphasia and/or AOS [Anticipated]

8. ARMS, GROUPS, AND INTERVENTIONS

Arm 1: Direct intervention Arm Type: Experimental

Arm Title: Multimodal Intensive Rehabilitation of Aphasia and Apraxia of Speech (MIRAA)

Arm description: Goal level 60 hours of intensive treatment during 6 weeks. Intensive

treatment of aphasia and AOS in ICAP-format (MIRAA).

Arm 2: Control Arm Type: No Intervention

Arm Title: Waiting group

Arm description: No intervention during 6 weeks, testing directly before and after the

waiting period. After the waiting period the participants receives the same intervention as the direct intervention arm.

9. OUTCOME MEASURES

Primary Outcome Measures

1. Evaluation of training, questionnaire to participating SLPs Minimum score 0, maximum score 12. Higher scores mean better outcome on satisfaction with intensive training and effects on speech, language and functional communication. [Time Frame: Directly after intensive treatment]

2. Evaluation of training, questionnaire to participants

Minimum score 3, maximum score 12. Higher scores mean better outcome on satisfaction with intensive training and effects on speech, language and functional communication. [Time Frame: Directly after intensive treatment]

Secondary Outcome Measures

3. Comprehensive Aphasia Test (CAT)

Comprehensive Aphasia Test (CAT) language battery. Comprehension of spoken language: minimum score 0, maximum score 66; Comprehension of written language: minimum score 0, maximum score 62; Repetition: minimum score 0, maximum score 74; Naming: minimum score 0, maximum score no limit; Reading: minimum score 0, maximum score 70; Writing: minimum score 0, maximum score 76. Higher scores mean better outcome in language functions. [Time Frame: Changes from baseline in language battery scores at 6 and 16 (+-2) weeks.] 4. Boston Naming Test (BNT)

Minimum score 0, maximum score 60. Higher scores mean better outcome in naming ability. [Time Frame: Changes from baseline scores at 6 and 16 (+-2) weeks.]

5. Rating scale for apraxia of speech (SkaFTA, Swedish version of ASRS) Minimum score 0, maximum score 52. Lower scores mean better outcome in speech functions.

[Time Frame: Changes from baseline scores at 6 and 16 (+-2) weeks.]

6. Protocol for Apraxia of Speech (TAX)

Minimum score 0, maximum score 30. Lower scores mean better outcome in speech functions and non-verbal oral apraxia. [Time Frame: Changes from baseline scores at 6 and 16 (+-2) weeks.]

7. Comprehensive Aphasia Test (CAT), subtest cognitive screening Minimum score 0, maximum score 38. Higher scores mean better outcome in cognitive functions. [Time Frame: Changes from baseline scores at 6 and 16 (+-2) weeks.]

8. Communicative Effectiveness Index (CETI)

Minimum score 0, maximum score 100. Higher scores mean better outcome in communicative effectiveness. [Time Frame: Changes from baseline scores at 6 and 16 (+-2) weeks.]

9. General Health Questionnaire 12 questions (GHQ-12) Minimum score 0, maximum score 36. Lower scores mean mean better outcome in general health. [Time Frame: Changes from baseline scores at 6 and 16 (+-2) weeks.]

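### The protocol plans no data from patients who decline, leave during the wait or stop MIRAA early, so the patient side of the compliance question rests mainly on those who stayed

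*Protocol*

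**What the plan says.** Protocol section 5 (Study Description) sets the aim: "The primary aim of this project is to explore the feasibility for national implementation of an intensive comprehensive intervention program". The first question beneath it begins "What are facilitating or hindering factors for SLPs and their patients in the subacute and chronic phase post stroke" and concerns complying with an intensive programme of this kind. Patients are named as well as SLPs.

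The sources of evidence are timed as follows.

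- Section 9 (Outcome Measures): both primary outcomes, the SLP questionnaire and the participant questionnaire, have the entry "Time Frame: Directly after intensive treatment". Each is scored so that "Higher scores mean better outcome on satisfaction with intensive training and effects on speech, language and functional communication". For the participant form the range is "Minimum score 3, maximum score 12".
- Section 5: "Following administration of the MIRAA-program including pre- and post-testing, participating SLPs will complete a questionnaire" about their experience of delivery and about what hindered or helped implementation.
- Section 5: a subgroup from five clinics takes part in semi-structured interviews combined with focus groups and "participant observations during one day of the last week of the intensive program".
- Section 5, on providers who did not join: "A group consisting of SLPs not being able to participate in the study will form a focus group", to discuss what stood in their way.

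Section 8 (Arms, Groups, and Interventions) gives 60 hours over six weeks as a goal level and has the control arm wait six weeks before receiving the same programme. Neither uptake, completion nor hours received appears among the outcomes in section 9.

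**The concern.** A question about what hinders patients from complying is best answered by those who did not comply. Under the timing as written, three groups of patients have no described route to give an answer: those who decline when offered the study, waiting-arm patients who leave before treatment begins, and those who start and stop before the end. Fatigue, travel or the load of the programme may be what removed them. If so, the strongest patient-level barriers are the ones most likely to be missing.

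The protocol deals with this on the provider side, through the focus group of SLPs who could not join, and has no counterpart for patients. The gap cannot be left to a statistical analysis plan: whom to ask and when is data collection, and an analysis cannot recover a questionnaire that was never given or a reason that was never written down. At stake is whether the conclusion on national feasibility describes all patients offered the programme or mainly those who saw it through.

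**Working it through.** **Step 1: who is covered by which source.** Set side by side, the described sources reach these groups.

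| Group | Described source of data on barriers or satisfaction |
|---|---|
| SLPs unable to take part | Focus group (section 5) |
| SLPs delivering MIRAA | Questionnaires after the programme; subgroup interviews (sections 5 and 9) |
| Patients present to the end | Participant questionnaire; subgroup interviews, focus groups, observations |
| Next of kin | Questionnaires and interviews (section 5); no separate provision when the patient declines or stops |
| Patients who start and stop early | None described; at most what an SLP reports |
| Waiting-arm patients who leave during the wait | None described; at most what an SLP reports |
| Eligible patients who decline | None described; at most what an SLP reports |

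The last three rows are the gap.

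**Step 2: is there a figure in the plan to reproduce?** No. Section 7 gives an anticipated enrolment of 70. The protocol states no dropout rate, no expected score and no feasibility threshold, so the size of any bias cannot be derived from it.

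**Step 3: illustration under stated assumptions.** Let p be the share of starters who stop early, C the mean score of completers and C − g the mean that stoppers would have given.

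- Mean over all starters = (1 − p) × C + p × (C − g) = C − p × g.
- Bias of the completers-only mean = C − (C − p × g) = p × g.

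The participant scale is 12 − 3 = 9 points wide. Assume p = 10, 20 or 30% and g = 0, 2 or 4 points, and take all 70 as starters:

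| p | Completers of 70 | g = 0 | g = 2 | g = 4 |
|---|---|---|---|---|
| 10% | 63 | 0 | 0.2 (2.2% of range) | 0.4 (4.4%) |
| 20% | 56 | 0 | 0.4 (4.4%) | 0.8 (8.9%) |
| 30% | 49 | 0 | 0.6 (6.7%) | 1.2 (13.3%) |

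At p = 20%, 70 − 56 = 14 starters would be absent from the participant outcome. Both p and g are assumptions. Decliners are outside this calculation because they are never enrolled.

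**Step 4: what the arithmetic does not capture.** The primary scores concern satisfaction and perceived effect. The barriers themselves come from the interviews and the questionnaires on experience. Losing stoppers' and decliners' own reasons does not depend on g: it occurs even where the score bias is zero.

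**The case against.** A reader might infer that only people who reach the end of MIRAA supply any data, and that feasibility is therefore overstated by a known amount. The documents do not support that reading.

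- SLPs who never joined are heard in their own focus group. SLPs who recruit and treat patients can report why some declined or stopped, and next of kin also contribute. This stands, and it limits the point to patients' own accounts.
- Reaching the last week is not the same as complying. The 60 hours are a goal and the content is adapted to each clinic and patient, so people who received far less may still be asked. This stands: partial compliers are inside the planned data, which is why the wording here is mainly those who stayed.
- The time-frame entry does not forbid giving the form to someone whose treatment ended in week 2, and the last-week phrase may belong to the observations alone and not to the interviews. Both are fair. But nothing in the protocol provides for the earlier use, and clinics on a list of 22 entries cannot be expected to read it in the same way.
- It might also be inferred that an SLP whose patient stops drops out of the primary outcome. The protocol does not say so; an SLP may still complete the form on other patients.
- The numerical bias is the product of two assumed quantities, and no feasibility threshold is stated for it to cross. This stands in full; the figures are illustrative only.
- Pooling answers given in week 2 with answers given in week 6 mixes different exposures in one mean. This stands and is met in the fix by separate reporting.

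**Conclusion.** The point holds for patients. The protocol asks what hinders them from complying but describes no data collection from those who decline, leave while waiting or stop early, and no outcome counts uptake, completion or hours received. The evidence on the patient side will come mainly from those who stayed, with second-hand reports from SLPs and next of kin for the rest. Feasibility is therefore likely to look better than it is. That is a plausible direction and not a demonstrated result: it rests on the assumption that people who stop or decline face stronger barriers, or would be less satisfied, than those who stay. The range of 0 to 1.2 points on the 9-point participant scale shows what assumed stopping of 10 to 30% and assumed gaps of 0 to 4 points would do. It is not an estimate for this trial. The change is cheap and should be made, because data not collected at the time cannot be recovered later.

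**What to change.** 1. In section 9, set the time frame of the participant and SLP questionnaires to the end of intensive treatment or the time of stopping it, whichever comes first. Report the scores for all starters, and separately for completers and early stoppers.
2. Have SLPs record the main reason when a consecutively offered eligible patient declines, leaves during the waiting period or stops. Report these counts together with completion and hours received against the 60-hour goal level.
3. Within the existing interview subgroup at the five clinics, include consenting early stoppers in place of some completers, so that no extra interviews are needed.

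Cost: revised protocol wording, the same forms given earlier to those who stop, and a small recording burden on SLPs. Mean scores will probably be slightly lower, and the answers will follow differing amounts of treatment, which is why completers and early stoppers should also be reported apart. Treatment and randomisation are unaffected.

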10. ELIGIBILITY

Sex/Gender:

Sex: All

Gender Based: No

Minimum Age: 18

Unit of time: Years

Maximum Age: No limit

Unit of time: Years

Accepts Healthy Volunteers: No

Eligibility Criteria:

Inclusion Criteria:

- Aphasia 3 months post stroke diagnosed by SLP
- Apraxia of Speech 3 months post stroke diagnosed by SLP
- Being able to participate in rehabilitation in Swedish (not in need of translator to take part in treatment).

Exclusion Criteria:

- Advanced cognitive decline
- Severe visual impairment
- Severe hearing-impairment

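### Does the inclusion list demand both aphasia and apraxia of speech, and would and/or recruitment dilute the apraxia outcomes?

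*Protocol*

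**What the plan says.** Protocol section 10 (Eligibility) has three inclusion bullets. The first two are "Aphasia 3 months post stroke diagnosed by SLP" and "Apraxia of Speech 3 months post stroke diagnosed by SLP". The third is "Being able to participate in rehabilitation in Swedish (not in need of translator to take part in treatment". No word joins the first two, and neither says whether three months is a minimum.

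Elsewhere the population is described inclusively. The brief title in section 1 is "implementation of intensive rehabilitation of aphasia and/or apraxia of speech in Swedish healthcare". The primary aim in section 5 speaks of "patients in the subacute and chronic phase post stroke with aphasia and/or AOS". Section 7 gives "Enrollment: 70 participants with aphasia and/or AOS [Anticipated". The section 5 text on recruiting speech-language pathologists (SLPs) also uses and/or for their caseload.

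Section 9 lists two AOS scales among the secondary outcomes: "Rating scale for apraxia of speech (SkaFTA, Swedish version of ASRS", scored 0 to 52, and TAX, scored 0 to 30. Lower is better on both, and both are taken as change from baseline. No analysis set is named for any scale. Section 5 says that everyone is tested before, after and at follow-up. Section 12 names a statistical analysis plan as a separate document.

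**The concern.** The Swedish-language bullet must hold for every participant, so the list invites a cumulative reading in which a patient with aphasia but no AOS is ineligible. That would contradict the population stated elsewhere. Section 5 lists 22 clinic entries and makes meeting the inclusion criteria the condition for being offered the study. If clinics read the list differently, they would recruit different kinds of patient. Section 7 calls the trial cluster randomized without naming the cluster; if clinics are the clusters, such differences could appear as case-mix imbalance between arms. The time wording raises a similar doubt, because a bare three months sits oddly beside an aim that covers the subacute and chronic phases.

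The and/or reading brings a second worry. A participant without AOS should start near the best possible SkaFTA and TAX scores and have little room to improve. If everyone is analysed, the mean effect on these scales would understate the effect in people with AOS, and power could fall. The mirror case is a person with AOS but no aphasia, who may be close to the top of CAT subscales or the BNT.

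**Working it through.** **Eligibility wording.** There is no figure to reproduce, so the sections are set side by side.

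- Section 10 contains neither *and* nor *or* between the two diagnoses. A requirement for both is an inference from the list format.
- Sections 1, 5 (twice) and 7 state and/or outright.
- Section 5 records aphasia type and severity, AOS and time since onset as background data. This fits a population in which diagnosis and time since stroke vary.
- Section 5 also gives participating SLPs a two-day workshop and recurring sessions that cover the study's logistics, so the criteria are not applied from the bullets alone.

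Only one reading agrees with every section: at least one of the two diagnoses, with three months as a lower limit.

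**Dilution.** The protocol gives N = 70 and two arms. It gives no AOS share, effect size, standard deviation, intracluster correlation or allocation ratio. Everything below is therefore assumed: 35 per arm, two-sided 5% test, clustering ignored, an effect of 0.8 SD in people with AOS and none in the rest.

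If a share p has AOS, the whole-group mean effect is p × 0.8:

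- 10 of 35: 10/35 × 0.8 = 0.23
- 14 of 35: 14/35 × 0.8 = 0.32
- 18 of 35: 18/35 × 0.8 = 0.41

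Power depends on how much scores vary in people without AOS. Simulation (20,000 trials, t-test) gives, as all participants versus AOS only:

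| AOS per arm | Non-AOS change SD 0.1 | SD 0.5 | SD 1.0 |
|---|---|---|---|
| 10 | 34% vs 40% | 23% vs 39% | 14% vs 39% |
| 14 | 48% vs 53% | 37% vs 52% | 24% vs 53% |
| 18 | 61% vs 65% | 52% vs 64% | 37% vs 64% |

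The AOS-only figures differ by a point between columns through simulation error. The loss is 4 to 6 points in the first column, 12 to 16 in the second and 25 to 29 in the third.

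A closed-form check of the limiting case, with no variation at all in people without AOS, uses a pooled SD of √(p + 0.5·p(1−p)·d²). For p = 0.5 and d = 0.8 this is √(0.5 + 0.5 × 0.25 × 0.64) = √0.58 = 0.762. The standardised effect is 0.40/0.762 = 0.525 and power is 59%, against 66% in the AOS group alone. For p = 0.3 the pair is 38% and 45%; for p = 0.7 it is 76% and 80%. The loss is again small, about 4 to 7 points.

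The first column and the closed-form case match the argument that people without AOS sit at the floor and cannot move. The larger losses need these people to vary substantially, which that argument denies.

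**The case for a change.** The strongest case for a change is that eligibility belongs in the protocol and not in an SAP, that section 10 is the text clinics apply, that recruitment is under way (section 2), and that rewording costs almost nothing. AOS status is already recorded at the first assessment, so naming an analysis group for each scale would also be cheap. Power was higher in the AOS-only analysis in every case run.

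Part of this stands. The connective is missing, the time wording has no direction, and section 10 would read better if it were brought into line with sections 1, 5 and 7. But nothing in the document suggests that any clinic is turning away patients with aphasia alone, and the case-mix argument needs clinics to diverge despite common training and four consistent statements of the population.

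On the outcomes, restriction by diagnosis is a choice and not a correction. Averaging over a consecutively recruited mixed population is a legitimate target, and the randomised comparison is not biased for it. Restriction also has costs. Section 9 says that TAX covers non-verbal oral apraxia as well as speech, so limiting it to people with AOS could drop some who have a deficit it measures. The mirror argument about ceilings cannot hold for CAT naming, which section 9 gives no upper limit.

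**Conclusion.** No change to the plan follows. The eligibility point is a clerical omission whose intended meaning is plain from the rest of the protocol; tidying the bullets would alter neither the intended population nor any result. The dilution point is conditional. It arises only if SkaFTA and TAX are analysed in everyone, which the protocol does not fix and the SAP may settle. It concerns secondary outcomes only, since the two primary outcomes are questionnaires.

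The size of any dilution cannot be derived from the document. Under the assumptions used (0.8 SD effect in people with AOS, none in others, 35 per arm, no clustering), the mean effect shrinks in proportion to the AOS share. The power lost against an AOS-only analysis is then 4 to 6 points when people without AOS barely change. It reaches 25 to 29 points only if their scores vary as much as those of people with AOS. This conclusion would weaken if there were evidence that clinics had read the list as requiring both diagnoses; the protocol contains none.
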